4.7 Medical History and Concomitant Illnesses

Medical history is assessed at screening and include prior and ongoing medical illnesses and conditions and prior surgical procedures not related to the primary diagnosis.

Medical History terms will be coded using MedDRA, 19.1. Medical History terms will be listed.

4.8 Prior and Concomitant Medications

Medications are all prescription medications, over-the-counter medications, or alternative therapies registered from screening through 30 days after the last dose of study drug. Medications will be listed (excluding those taken prophylactically for Pan-HER reactions).

PAREXEL International
Statistical Analysis Plan Template for Early Phase Studies

Symphegen A/S
Sym013-01

Medications will be coded using the World Health Organization Drug Dictionary drug (WHODD, September 2016 and will be presented by WHODD Anatomical-Therapeutic-Chemical (ATC) therapeutic classification and preferred term (PT).

Medications and treatments administered prior to the first infusion of study drug which stopped prior to first infusion of study drug will be considered as prior medications and flagged in the listing.

Medications and treatments which started before, on or after the first infusion of study drug and which stopped after first infusion of study drug (including medications and treatments which stopped the day of first infusion) will be considered as concomitant medications.

If medication start and/or stop dates are missing or partial, the dates will be compared as far as possible with the date of first dose of study medication. Medications will be assumed to be concomitant, unless there is clear evidence (through comparison of partial dates) to suggest that the medication stopped prior to the first dose of study medication. If there is clear evidence to suggest that the medication stopped prior to the first dose of study medication, the medication will be assumed to be Prior.

Prophylactic treatment for Pan-HER related reactions and pre-medication for Pan-HER infusions will be listed separately.

Concomitant procedures performed during the study will be collected and listed.

4.9 Treatment Exposure and Compliance

Data of study drug infusion including dose reduction and interruption information, patient drug administration irregularities (dose reduction and interruption) and infusion related reaction will be listed.

Duration of the Pan-HER exposure, treatment duration, actual number of doses, planned total dose, actual total dose and Relative Dose Intensity (RDI) will be derived as follow:

- Duration of exposure (days) = (last dose date - first dose date +1)
- Actual Treatment duration (weeks) =

PAREXEL International
Statistical Analysis Plan Template for Early Phase Studies

Symphogen A/S
Sym013-01

(last dose date - first dose date + 7) / 7 for weekly dose (i.e. dose regimen Q1W), or
(last dose date - first dose date + 14) / 7 for biweekly dose (i.e. dose regimen Q2W)

- Number of treatment cycles initiated (i.e. at least one infusion for the cycle)
- Number of treatment cycles completed (i.e. all cycle infusions were received by the patient)
- Planned total number of doses for Q1W = (Date of last dose – Date of first dose +1) / 7 rounded up to integer
- Planned total number of doses for Q2W = (Date of last dose – Date of first dose +1) / 14 rounded up to integer
- Planned total dose = Planned dose * Planned total number of doses
- Planned treatment duration (weeks) for Q1W = Planned total number of doses × 1
- Planned treatment duration (weeks) for Q2W = Planned total number of doses × 2
- Relative dose intensity (RDI)

$$RDI (\%) = 100 \times \frac{\text{Sum of all received dose / Duration of exposure (days)}}{\text{Total planned dose / (Planned treatment duration (weeks) \times 7)}}$$

whereas the total planned dose (mg/kg) and planned dose duration are calculated based on the number of doses of the study medication a patient had received at the initially planned dose (mg/kg) for the cycle according to the planned dosing schedule.

Example, if a patient received 8 bi-weekly (i.e. dose regimen Q2W) doses of a study medication with a loading dose of 12 mg/kg and rest 9 mg/kg, with 1 dose reduction from 9 mg/kg to 6 mg/kg starting at week 14 and 1 week delay and at week 16, then

$$RDI (\%) = 100 \times \frac{(12 + 5 \times 9 + 2 \times 6) / 119}{(12 + 7 \times 9) / 112} = 86.6\%$$

The number of initiated and completed cycles of taking Pan-HER will be summarized both as categoric (0, 1, 2, 3, 4, 5, >5) and continuous parameter.

PAREXEL International
Statistical Analysis Plan Template for Early Phase Studies

Sympogen A/S
Sym013-01

Duration of the Pan-HER exposure will be summarized as actual treatment duration (weeks) and actual number of doses. RDI will be summarized both as categoric (> 100%; 90 % - 100 %; 80 % - < 90%; 70 % - < 80%) and continuous parameter. Swimmer Plot will be presented showing Treatment Duration together with Tumor Response data.

Number of patients who had dose reduction (Any, 1, 2, 3+ times) and dose interruption (Any, 1, 2, 3+ times)) will be summarized.

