6 TABLES, FIGURES AND LISTINGS

All the Tables, Figures and Listings with asterisk will be included in the CSR.

Table 14.1.1 Patient Enrollment (All Consented Patients) *

Table 14.1.2 Patient Disposition by Treatment Schedule and Dose Group (Full Analysis Set) *

Table 14.1.3 Patient Demographics and Baseline Characteristics (Full Analysis Set) *

Table 14.1.4 Cancer Baseline Characteristics (Full Analysis Set)

Table 14.1.5 Prior Cancer Therapies (Full Analysis Set)

Table 14.2.1.1 Serum Concentration of the six monoclonal antibodies in Pan-HER for single and repeated dose PK profiles (Full Analysis Set) *

Table 14.2.1.2 Peak and Trough Serum Concentration of the six monoclonal antibodies in Pan-HER by Study Day (Full Analysis Set) *

Table 14.2.2 Serum PK Parameters for the six monoclonal antibodies in Pan-HER (Full Analysis Set) *

Table 14.2.3.1 Biomarkers from Skin Biopsy (Full Analysis Set) *

Table 14.2.3.2 Biomarkers from Tumor Biopsy (Full Analysis Set) *

Table 14.2.4.1 Best Overall Response Objective Response and Disease Control Rate (Full Analysis Set) *

Table 14.2.4.2 Time to Progression (Full Analysis Set) *

Table 14.2.4.3 Maximal Reduction in Sum of Diameters of Target Lesion from Baseline (Full Analysis Set)

Table 14.2.4.4 Maximal Reduction in Sum of Diameters of Target Lesion from Baseline by Primary Tumor Type (Full Analysis Set)

Table 14.2.4.5 Number of Treatment Cycles (Full Analysis Set) *

PAREXEL International
Statistical Analysis Plan Template for Early Phase Studies

Symphogen A/S

Sym013-01

Table 14.2.4.6 Treatment Duration and Dose Intensity (Full Analysis Set) *

Table 14.2.4.7 Dose Reduction, Interruption, and Delay (Full Analysis Set) *

Table 14.2.4.8 Dose-Limiting Toxicity (DLT Set) *

Table 14.3.1.1 Overall Summary of TEAEs (Full Analysis Set) *

Table 14.3.1.2 TEAEs by SOC and PT (Full Analysis Set) *

Table 14.3.1.3 Related TEAEs by SOC and PT (Full Analysis Set) *

Table 14.3.1.4 TEAEs by SOC and PT and Worst CTCAE Grade (Full Analysis Set) *

Table 14.3.1.5 Related TEAEs by SOC and PT and Worst CTCAE Grade (Full Analysis Set) *

Table 14.3.1.6 Serious TEAEs by SOC and PT (Full Analysis Set) *

Table 14.3.1.7 Related Serious TEAEs by SOC and PT (Full Analysis Set) *

Table 14.3.1.8 TEAEs Leading to Permanent Discontinuation of IMP by SOC and PT (Full Analysis Set) *

Table 14.3.1.9 Related TEAEs Leading to Permanent Discontinuation of IMP by SOC and PT (Full Analysis Set) *

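### The relative dose intensity formula in SAP 4.9 leaves out the last dosing interval, contradicts its own worked example (97.2% against 86.6%), and has no band below 70%

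*SAP*

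**What the plan says.** SAP 4.9 gives two measures of time on drug. The first is "Duration of exposure (days) = (last dose date - first dose date +1"). The second, Actual Treatment duration, adds a full dosing interval after the last dose: + 7 days for Q1W and, for Q2W, ("last dose date - first dose date + 14) / 7 for biweekly dose (i.e. dose regimen Q2W").

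The RDI formula uses the first measure. Its numerator is "Sum of all received dose / Duration of exposure (days"). Its denominator is the total planned dose divided by the planned duration in days, and the planned duration counts whole intervals: "Planned treatment duration (weeks) for Q2W = Planned total number of doses × 2" (× 1 for Q1W).

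A worked example follows: "if a patient received 8 bi-weekly (i.e. dose regimen Q2W) doses of a study medication with a loading dose of 12 mg/kg", the others at 9 mg/kg, the last two reduced to 6 mg/kg, and one delay of a week. It divides 69 mg/kg by 119 days and 75 mg/kg by 112 days and reports 86.6%.

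The section then states that "Duration of the Pan-HER exposure will be summarized as actual treatment duration (weeks) and actual number of doses", and that RDI is shown as a continuous variable and as "categoric (> 100%; 90 % - 100 %; 80 % - < 90%; 70 % - < 80"%). SAP 6 marks "Table 14.2.4.6 Treatment Duration and Dose Intensity (Full Analysis Set") for inclusion in the abbreviated report.

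**The concern.** RDI compares a received dose rate with a planned dose rate, so both need the same convention for the interval after the last dose. Here the planned rate includes that interval and the received rate includes one day of it. Every patient's RDI is pushed up, and most strongly after few doses, which is where early stopping in a dose-escalation study places patients. A patient whose doses were reduced or delayed can then appear in the band above 100%.

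The formula and the example cannot both be followed, and the SAP does not say which governs. SAP 4.14, on changes to the planned analysis, is silent on this. Separately, a patient whose RDI is below 70% has no row in the categorical summary.

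**Working it through.** **1. The SAP's own example.** Inputs from SAP 4.9: 8 Q2W doses and one 1-week delay.

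- First to last dose: 7 × 14 + 7 = 105 days.
- Received: 12 + 5 × 9 + 2 × 6 = 69 mg/kg. Planned: 12 + 7 × 9 = 75 mg/kg.
- Planned doses by the date rule: 106/14 = 7.6, rounded up to 8, which is also the number received. Planned duration: 8 × 2 × 7 = 112 days.
- As printed: 100 × (69/119)/(75/112) = 86.6%. The 119 days are 105 + 14, which is Actual Treatment duration × 7.
- As defined: 105 + 1 = 106 days, so 100 × (69/106)/(75/112) = 97.2%.

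The gap is 10.6 points and moves the patient from the 80 to <90% band to the 90 to 100% band. Other readings of the +1 rule do not rescue the printed figure: leaving the delay out of the span gives 99 days and 104.1%; reading the span as week 0 to week 17 gives 120 days and 85.9%.

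**2. General form.** Take a constant planned dose D, interval I (7 or 14 days), n full doses and cumulative delay d days. The planned rate is D/I per day whatever the planned number of doses, because that number cancels. Then:

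- Written: 100 × I × n / (I(n − 1) + d + 1)
- With the last interval included: 100 × I × n / (I × n + d)

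With d = 0:

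| Doses | Q1W, written | Q2W, written | Either, with last interval |
|---|---|---|---|
| 1 | 7/1 = 700% | 14/1 = 1400% | 100% |
| 2 | 14/8 = 175% | 28/15 = 187% | 100% |
| 4 | 28/22 = 127% | 56/43 = 130% | 100% |
| 8 | 56/50 = 112% | 112/99 = 113% | 100% |

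The written form falls to 100% only when d = I − 1, that is 6 days of accumulated delay for Q1W or 13 for Q2W, for any n.

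**3. Reduced or delayed dosing (illustrative Q2W patients, two doses, planned 9 mg/kg).**

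| Case | Written | With last interval |
|---|---|---|
| Both full, second 1 week late | 28/22 = 127.3% | 28/35 = 80.0% |
| 9 then 6 mg/kg, on time | (15/15)/(9/14) = 155.6% | (15/28)/(9/14) = 83.3% |
| 9 then 6 mg/kg, 1 week late | (15/22)/(9/14) = 106.1% | (15/35)/(9/14) = 66.7% |

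All three fall above 100% as written. None does once the last interval is counted.

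**4. Values below 70%.** Protocol Table 9 lists Dose Level 2 (2 mg/kg) as the first reduction from Dose Level 3 (4 mg/kg). One such reduction from dose 2 of 8 on-time weekly doses gives 4 + 7 × 2 = 18 mg/kg, so (18/50)/(4/7) = 63.0% as written and (18/56)/(4/7) = 56.3% with the last interval. Neither value has a category.

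**The case against.** The intent can be recovered from the same section. Actual Treatment duration is defined there, the example uses it, and exposure is to be summarized by it. A programmer who tests code against the example would see the mismatch, SAP 4.1 requires outputs to be independently checked, and a value of 1400% would show as the maximum of the continuous summary. That lowers the chance of the error reaching the report. It does not correct the text, and the milder distortions, such as 106.1% for 66.7%, would not look odd on the page.

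The example has a loading dose, which no listed Part 1 dose level uses, and it covers Q2W only. The 97.2% against 86.6% therefore proves an inconsistency and is not an effect on an enrolled patient. The Q1W conflict follows from the parallel + 7 definition.

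The other magnitudes are hypothetical. The documents give no distribution of doses received, so the number of patients who would change band is unknown. The 4 to 2 mg/kg case shows only that values below 70% are possible: for that cohort Protocol 3.2.4.1 describes Grade 1–2 infusion reactions, mucositis and diarrhea, while the non-hematologic reduction triggers in Protocol 7.1.4.3 that are defined by grade start at Grade 3.

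RDI is also descriptive. It is not among the endpoints in SAP 3.2, and Table 14.2.4.7 and Listings 16.2.5.1 and 16.2.5.2 show reductions, interruptions, delays and administration directly. The missing band is a smaller display matter, since such patients stay in the continuous summary. These points limit the consequence; the contradiction remains.

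**Conclusion.** The concern holds. As written, the RDI formula omits 6 days (Q1W) or 13 days (Q2W) from the received side and contradicts the SAP's only worked example by 10.6 percentage points. For a constant planned dose, full on-schedule dosing reads 112% to 700% (Q1W) or 113% to 1400% (Q2W) over 8 down to 1 doses. The percentages for individual dosing patterns are illustrations, not estimates for enrolled patients. The lack of a band below 70% is a separate, minor gap.

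The effect is confined to a descriptive exposure table that is kept for the abbreviated report. The DLT endpoint and the MTD are untouched. It should be fixed before that table is produced.

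**What to change.** In the RDI numerator, replace Duration of exposure (days) with Actual Treatment duration (weeks) × 7, that is last − first + 7 days for Q1W and last − first + 14 days for Q2W. This reproduces 86.6% and returns exactly 100% for full dosing on schedule. Add a band for RDI below 70%.

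A table footnote would help the reader, although its absence is not an error: RDI covers only the time on treatment, so a patient who stops after one full dose still reads 100% after the correction, and the table should be read with Table 14.2.4.7 and the disposition output.

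The cost is one substituted term, one added category and one footnote, in the SAP and in the program for Table 14.2.4.6. No new data are needed.

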4.10 Efficacy Evaluation

4.10.1 Analysis and Data Conventions

No formal testing of hypotheses has been planned in this study. Therefore, no formal sample size calculations were performed.

Two-sided Confidence Intervals will be presented with $\alpha=0.05$ (95% CI).

4.10.1.1 Multi-center Studies

There will not be any adjustment for study centers, subgroup analysis based on study centers are not planned.

4.10.1.2 Adjustments for Covariates

No statistical models will be provided for the analysis of Study Endpoints. All study analyses will be descriptive and will be seen from an exploratory perspective. No adjustment for covariates is then expected.

4.10.1.3 Handling of Dropouts or Missing Data

Efficacy data that are reported as missing will be excluded from all descriptive and non-descriptive data analysis. There will be no imputation of missing efficacy data.

For general rules about handling of missing data refer to section 4.2.

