PR	NE	SD provided minimum criteria for SD duration met, otherwise NE
NE	NE	NE

CR = complete response, PR = partial response, SD = stable disease, PD = progressive disease, and NE = inevaluable.

a If a CR is truly met at first time point, then any disease seen at a subsequent time point, even disease meeting PR criteria relative to baseline, makes the disease PD at that point (since disease must have reappeared after CR). Best response would depend on whether minimum duration for SD was met. However, sometimes 'CR' may be claimed when subsequent scans suggest small lesions were likely still present and in fact the patient had PR, not CR at the first time point. Under these circumstances, the original CR should be changed to PR and the best response is PR.

Patients with non-target disease only, may have a time point response of NON-CR/NON-PD, these responses will be included in the count of SD.

Determinations of Best Overall Responses derived as described will be reviewed by Symphogen and PAREXEL on a patient by patient basis across time.

- Unconfirmed BOR by RECIST v1.1:

Per RECIST 1.1 [1]: in cases where confirmation of complete or partial response is not required the Best response is defined as the best response across all time points (for example, a patient who has SD at first assessment, PR at second assessment, and PD on last assessment has a best overall response of PR). When SD is believed to be best unconfirmed response, it must also meet the protocol specified minimum time from baseline.

PAREXEL International
Statistical Analysis Plan Template for Early Phase Studies

Symphegen A/S
Sym013-01

Patients with non-target disease only, may have a time point response of NON-CR/NON-PD, these responses will be included in the count of SD.

- Documented objective response (OR) confirmed and unconfirmed, based on determination of confirmed and unconfirmed best overall response (BOR) per RECIST v1.1.

Confirmed OR is defined as the percentage of patients who had confirmed CR or PR.

Unconfirmed OR is defined as the percentage of patients who had unconfirmed CR or PR.

'The duration of overall response is measured from the time measurement criteria are first met for CR/PR (whichever is first recorded) until the first date that recurrent or progressive disease is objectively documented (taking as reference for progressive disease the smallest measurements recorded on study). ' [1].

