Duration of Response (weeks) = (Date of PD – Date of first CR/PR [whichever is first recorded] + 1) / 7

- Time to Progression (TTP)

Time to documented PD (based on radiological assessments) will be derived and expressed in the unit of weeks. TTP is defined as the time from first dose of study drug until objective tumor progression; TTP does not include deaths [3]. Based on this definition, PDs will be counted as outcome; patients with last tumor assessment showing CR or PR or SD will be censored at the time of last available tumor assessment per RECIST v1.1; patients who died for any cause (including deaths of disease but with no documented PD) will as well be censored at the time of last available tumor assessment per RECIST v1.1.

TTP (weeks) = (Date of PD – Date of first IMP infusion + 1) / 7

In this study, there is no planned survival status after discontinuation of study treatment, therefore, progression-free survival is not calculated.

PAREXEL International
Statistical Analysis Plan Template for Early Phase Studies

Symphogen A/S
Sym013-01

- Disease control rate (DCR), based on determination of confirmed BOR per RECIST v1.1.

The DCR is defined as the percentage of patients who had confirmed BOR of CR, PR or SD of at least 16 weeks. Definition of duration of TTP corresponds to SD duration; thus, these times will be used to determine if a patient was in SD for at least 16 weeks.

- Changes in sum of diameters of target lesions from baseline to end of trial participation

For patients with measurable disease (i.e., with target lesions), absolute and percent changes in the sum of diameters of target lesions from baseline to end of trial participation will be calculated, the best change will be identified as largest reduction or smallest increase.

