Categorical data will be summarized in terms of the number of patients providing data at the relevant time point (n), frequency counts and percentages. Any planned collapsing of categories will be detailed in the SAP text and the data displays. Percentages will be calculated using n as the denominator. Changes from baseline in categorical data will be summarized using shift tables where appropriate.

PAREXEL International
Statistical Analysis Plan Template for Early Phase Studies

Symphogen A/S
Sym013-01

The following rules will apply to all descriptive statistic displays, except the PK concentrations and parameters that are reported in significant digits described in section 4.10.4.4 below, where d denotes the decimal places in the original reported value:

- n : 0 decimal places (d.p.)
- Mean: $d + 1$ d.p.
- Confidence Interval: $d + 1$ d.p.
- SD: $d + 2$ d.p.
- Median: $d + 1$ d.p..
- Minimum: d .
- Maximum: d .
- Statistics in percentage: 1 d.p.
- p-value: 4 d.p.
- Except for p-value, a maximum of 3 decimal places will be displayed.

P-values greater than or equal to 0.001, in general, will be presented to three decimal places. P-values less than 0.001 will be presented as “<0.001”.

Details for reporting of statistical summaries specific to PK are detailed in section 4.10.1.4.

Figures

If not otherwise specified, each figure will be presented separately for the two dose regimens (Q1W and Q2W) with differentiate legend to discriminate the dose groups within the regimen; moreover, an overall figure will also be presented with differentiate legend to discriminate the two dose regimens. In the end, there will be three panel for each figure: first panel will show all patients, second panel patients in Q1W regimen, third panel patients in Q2W regimen.

All figures will be produced in black and white.

PAREXEL International
Statistical Analysis Plan Template for Early Phase Studies

Symphogen A/S
Sym013-01

Specification for PK figures will be detailed in section 4.10.4.1.

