4.5 Analysis Sets

Two analysis sets will be defined in accordance with the consolidated ICH E9 GCP guidelines.

The Full Analysis Set (FAS) will comprise all enrolled patients who have received at least one dose of Pan-HER. The FAS will be used for evaluation of all endpoints except evaluation of DLTs. The patients in the FAS will contribute to the analyses as allocated to treatment (patients will be reported below the regimen and dosage actually received). For the evaluation of PK endpoints, patients, full profiles, or single measurements can be excluded from the analyses with justification. The decision of excluding patients, full profiles, or part of profiles will be described in the clinical trial report (CTR).

The DLT Analysis Set will comprise all patients in the FAS enrolled in Part 1, except patients who did not complete Cycle 1 for reasons other than drug toxicity. The DLT Analysis Set will be used for evaluation of DLTs and the MTD or lack thereof.

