4.10.2 Analysis of Efficacy Variable(s)

All statistical analysis of the efficacy endpoints will be presented using the FAS.

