4.10.2.1 Anti-Tumor Response according to RECIST v1.1

The following anti-tumor response endpoints will be measured in Part 1:

- Confirmed and unconfirmed BOR by RECIST v1.1 will be listed and summarized by dose regimen and dose level received using frequency distribution for the categories CR, PR, SD, PD, and Not Evaluable.
- Number and percentage of patients with documented confirmed and unconfirmed OR will be summarized by dose regimen and dose level using frequency distribution with the corresponding 95% exact Clopper-Pearson Confidence Intervals (CI) for binomial proportion. All documented ORs will be listed including duration (weeks) of response.
- Patients in DCR will be listed and summarized by dose regimen and dose level using frequency distribution with the corresponding 95% exact Clopper-Pearson Confidence Intervals (CI) for binomial proportion.
- Time to Progression (TTP)

PAREXEL International
Statistical Analysis Plan Template for Early Phase Studies

Symphogen A/S
Sym013-01

The median TTP, as well as 26 weeks and 52 weeks TTP rates and the corresponding 95% CIs will be estimated using the product-limit method and presented using a Kaplan-Meier plot. Number and percent of censored patients will be presented, also number and percent of patients censored for death will be presented.

- Changes in sum of diameters of target lesions from baseline to end of trial participation
Changes in the sum of diameters of target lesions from baseline to end of trial participation will be listed as percentage and absolute value, the best change (i.e., largest reduction or smallest increase) will be identified and presented using summary table and plotted with a waterfall plot. Change in sum of diameters will also be presented by primary tumor type.
- Results of the tumor evaluation by CT/MRI for target lesions, non-target lesions and timepoint tumor response will be listed, as well as derived target and non-target time point responses.

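### The SAP's missing-data and denominator rules conflict with its FAS commitment for BOR, OR and DCR, and no rule assigns NE to a dosed patient with no post-baseline scan

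*SAP*

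**What the plan says.** Two sets of statements in the SAP bear on the denominator.

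The first set works by exclusion. Section 4.10.1.3 states: "Efficacy data that are reported as missing will be excluded from all descriptive and non-descriptive data analysis". It rules out imputation of efficacy data and refers to 4.2 for general rules. Section 4.2 states: "Categorical data will be summarized in terms of the number of patients providing data at the relevant time point (n), frequency counts and percentages". It adds: "Percentages will be calculated using n as the denominator".

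The second set works by analysis set. Section 4.10.2 states: "All statistical analysis of the efficacy endpoints will be presented using the FAS". Section 4.5 defines that set: "The Full Analysis Set (FAS) will comprise all enrolled patients who have received at least one dose of Pan-HER". No scan is required for membership. In Section 6, Table 14.2.4.1 (BOR, OR and DCR) is labelled Full Analysis Set and carries the asterisk that keeps it in the abbreviated study report.

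The endpoint definitions in 3.2.1.1 name no denominator. For OR: "Confirmed OR is defined as the percentage of patients who had confirmed CR or PR". For DCR: "The DCR is defined as the percentage of patients who had confirmed BOR of CR, PR or SD of at least 16 weeks". Under 4.10.2.1, BOR is tabulated "using frequency distribution for the categories CR, PR, SD, PD, and Not Evaluable". The endpoint list in 3.2 also restricts OR to patients with measurable disease, a restriction that 4.10.2 does not repeat.

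**The concern.** A dosed patient with no post-baseline tumor assessment belongs to the FAS but provides no response data. Under 4.10.2 that patient is in the denominator. Under 4.10.1.3 and 4.2, read as written, that patient is not. Two programmers following the same SAP could therefore produce different OR and DCR percentages and different exact confidence intervals.

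The two readings do not differ at random. A patient with no scan cannot have a documented CR, a documented PR, or SD lasting 16 weeks, so never adds to a numerator. Removing such patients can only raise a non-zero rate. What is at stake is the table that serves the secondary objective of a preliminary look at antitumor effect. It is reported by regimen and dose level, where groups are very small.

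**Working it through.** **Step 1. Does any rule send a patient with no scan to NE?**
- SAP 3.2.1.1, Table 3 (confirmed BOR): every row starts from a recorded response at a first time point. NE results only from rows such as NE then NE, or CR or PR then NE with the minimum SD duration unmet.
- SAP 3.2.1.1, unconfirmed BOR: the best response across time points. It is undefined when there are none.
- Protocol Appendix 1: its lost-to-follow-up example gives NE to a patient who already has one SD assessment.
- SAP 4.10.2.1: lists a Not Evaluable category but does not say who enters it.

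So NE is available for a patient with no assessment, but no text assigns it.

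**Step 2. Who could have no post-baseline scan?**
The first routine scan is at the end of Cycle 2, about 2 × 28 = 56 days after first dose. SAP 3.2.1.1 and Protocol 8.3.1 also schedule a scan on suspected progression, at EOT if more than 3 weeks have passed since the last one, and at the one-month follow-up if progression is not yet documented. A patient with a recent baseline scan who stops very early is not due an EOT scan, but is due the follow-up scan. Those left are mainly early deaths, withdrawals of consent and missed scans.

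**Step 3. How large is the effect?**
The documents give no expected OR or DCR, no dropout rate and no formal sample size (SAP 4.13), so there is no stated figure to reproduce. Let N be the FAS size, m the number with no scan, x the number meeting the endpoint, and d = m/N.
- FAS rate: x/N
- Rate under exclusion: x/(N − m)
- Ratio: N/(N − m) = 1/(1 − d)

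The ratio is 1/0.9 = 1.11 at d = 10%, 1/0.8 = 1.25 at 20% and 1/0.7 = 1.43 at 30%.

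Take N = 34, the approximate planned Part 1 size (Protocol 5.5), with m rounded to 3, 7 and 10. The values of x and d are assumptions, and the OR rows assume that all patients have measurable disease. Intervals are 95% exact Clopper-Pearson, as SAP 4.10.2.1 specifies.

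| Example | FAS, N = 34 | m = 3, n = 31 | m = 7, n = 27 | m = 10, n = 24 |
|---|---|---|---|---|
| OR, x = 3 | 8.8% (1.9–23.7) | 9.7% (2.0–25.8) | 11.1% (2.4–29.2) | 12.5% (2.7–32.4) |
| DCR, x = 8 | 23.5% (10.7–41.2) | 25.8% (11.9–44.6) | 29.6% (13.8–50.2) | 33.3% (15.6–55.3) |

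With the 19 patients entered by Amendment 6 (Protocol 3.2.4.1) and x = 3, the rate moves from 15.8% (3/19) to 17.6% (3/17), 20.0% (3/15) or 23.1% (3/13).

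Within a dose group, one patient without a scan turns 1/3 = 33.3% into 1/2 = 50.0%, or 1/6 = 16.7% into 1/5 = 20.0%. Two turn 1/6 into 1/4 = 25.0%.

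**Step 4. The second denominator question.**
Measurable disease is an entry criterion for Part 2 only (Protocol 6.1, criterion 8). Part 1 may therefore include patients with non-target disease only, for whom SAP 3.2.1.1 supplies a separate response table. Section 3.2 leaves them out of OR; 4.10.2 read alone includes them.

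**The case against.** The best defence is that the specific text favours the FAS. Section 4.10.2 governs efficacy, the FAS needs only one dose, and the table itself is labelled FAS. OR and DCR are percentages of patients, not of evaluable patients. The denominator rule in 4.2 speaks of data at a relevant time point, which suits visit tables better than a once-per-patient endpoint such as BOR. Section 4.10.1.3 excludes data and does not say that patients leave the analysis set. BOR has a Not Evaluable category, and BOR determinations are reviewed patient by patient.

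All of that stands as showing that the conservative reading is permitted. It does not show that it is required. Naming the FAS fixes who is eligible for the table; it does not cancel an explicit instruction that percentages use n, and 4.10.1.3 reaches all descriptive analysis. Patient-by-patient review without a stated rule leaves the choice open.

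It is also fair that the consequence is modest. Part 1 efficacy is secondary and descriptive, Part 2 did not take place, and the RP2D rests on safety, PK and target engagement. The per-patient response listings are in the report, so a reader could recompute the rates.

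**Conclusion.** The point holds as an unresolved conflict that can inflate OR and DCR. The direction is certain if the exclusion rule is applied and at least one patient meets the endpoint. The size is 1/(1 − d), or 1.11 to 1.43 over an assumed no-scan share of 10% to 30%. The documents give no value for d, and the extra scheduled scans argue against assuming a high one. No hypothesis test, error rate or dose decision is affected.

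A reader might infer four stronger things that the documents do not support:
- That the SAP certainly removes these patients. The FAS statement and the Not Evaluable category allow them to be kept.
- That everyone who stops before the end of Cycle 2 has no response assessment. The suspected-progression, EOT and follow-up scans should capture most of them.
- That as many as 10 of 34 patients would be lost. That is only the upper end of an assumed range.
- That the bias is worse at higher doses. No discontinuation rates by dose are given. Of the two patients with dose-limiting events at 9 mg/kg Q2W, Protocol 3.2.4.1 reports that one was discontinued and the other was retreated at a reduced dose.

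It still merits correction because it concerns a stated rule in conflict with the analysis set, in a table that will be produced for the abbreviated report.

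**What to change.** Add to SAP 4.10.1.3:
- FAS patients with no post-baseline tumor assessment are assigned BOR = NE. They stay in the denominator, counting as non-responders for OR and as not disease-controlled for DCR.
- The denominator for BOR and DCR is all FAS patients. For OR it is all FAS patients with measurable disease at baseline, which reconciles 3.2 with 4.10.2.
- The exclusion of missing efficacy data, and the use of n as denominator in 4.2, do not apply to BOR, OR or DCR. Exclusion is limited to the continuous change-in-diameter summaries. TTP keeps its own censoring rule in 3.2.1.1.

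The cost is a short text change, with no new data. The downside is slightly less favourable descriptive rates.
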